## 4.3. Trial design

Two randomized-controlled trials will be conducted; a dose-ranging study (trial A) and a parallel group study (trial B), with seven and three treatment arms, respectively to be followed-up each over a 21-28 days period. The second comparative trial will be conducted as a non-inferior study with a non-inferiority margin of 10%-points.

- (A) The DF study (Figure 1, top) is designed as a seven-armed trial including arms with ascending dose administration of moxidectin: 2 mg, 4 mg, 6 mg, 8 mg, 10 mg, 12 mg and a placebo-arm.
- (B) The parallel group study (Figure 1, bottom) is designed as a two-armed trial including one arm with a single drug administration of a standard dose of ivermectin (200  $\mu$ g/kg) and one arm with a treatment of a single best dose of moxidectin (8 mg, according to the findings in (A)). The optimal dose of findings in (A) are evaluated as the dose that is high enough to demonstrate efficacy in the target population, yet low enough to minimize safety concerns and adverse events.

#### The two study cohorts are presented in the figures below:

Figure 1. Design and timeline of the DF trial (top) and the parallel group trial (bottom) to be implemented. All sample sizes assume a drop-out of 10 %.

#### 4.3.1. Baseline larval count

At baseline, all participants will be asked to provide three stool samples (if possible on three consecutive days or otherwise within a total maximum of 6 days) [23, 24]. The stool samples Page **18** of **45** 

will be collected until a total of 210 and 350 *S. stercoralis*-infected adults are registered (two out of three stool samples show more than 0.4 LPG (trial A) or 0.1 LPG (trial B), in 10 g of stool sampled per person and time point) in the two studies, respectively. As diagnosing very low-intensity chronic infections remains a major challenge for quantitative and qualitative analysis for *S. stercoralis* only low/moderate to high infection patients are included in trial A (LPG >0.4 on two out of three samples). This inclusion criterion has been shown to result in a diagnostic sensitivity of more than 97% to close to 100%. [24].

Firstly, a quantitative Baermann funnel concentration technique will be used for the quantitative assessment of *Strongyloides stercoralis* infections [24-26] using stool samples from three different (optimal consecutive) days. 5 g stool sample (the stool container with the sample will be weighted before and after the Baermann test was set up) will be placed on gauze inserted into a glass funnel and covered with preheated water to 36°C. Following two hours of artificial light exposure, the collected liquid will be centrifuged and the sediment prepared for analysis by microscope. Duplicate Baermann will be prepared from each stool sample [27, 28]. Secondly, from two stool samples from each participant a duplicate Kato-Katz thick smear will be prepared to detect co-infection with any of the three major soil-transmitted helminthic infections (STHs), namely *Ascaris lumbricoides, Trichuris trichiura* and the hookworms (*Necator americanus* and *Ancylostoma duodenale*) [29]. If additional coinfections are observed, they will be assessed likewise.

The slides from the Baermann and Kato-Katz thick smears will be analyzed under a microscope by experienced technicians and a subsequent independent quality control of sample results (approximately 10%) will be conducted. *S. stercoralis* larvae will be counted quantitatively and eggs recorded for the different helminths species separately and qualitatively assigned as egg positive or negative. Results are considered correct if the following tolerance margin is not exceeded: (i) No difference in presence/absence *S. stercoralis*, (ii) egg/larvae counts are +/-10 eggs/larvae for counts <100 eggs/larvae or +/-20% for counts >100 eggs/larvae (for each species separately) [30]. In case discrepancies above the tolerance margin are noted in one or more slides, all slides are re-read by the local technicians. The new results are discussed, so that in case of discordant results, slides can be re-evaluated to reach consensus. Infection intensity expressed as the arithmetic and geometric mean egg/larvae count per gram of stool will be calculated for each treatment arm. All microscopically analyzed Baermann samples as well as the Kato-Katz thick smears will be destroyed within one day (after passing the quality control).

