	
 
to compare the larvae reduction rate (LRR) of the different treatment regimens against S. stercoralis (trial A and B).
 
	
	
 
4) trial A: to determine an exposure- (including Cmax, AUC and tmax) -response correlation of moxidectin in adults.
 
	
	
 
trial A: to compare the exposure-response of moxidectin using venous and capillary blood.
 
	
	
 
6) to evaluate the cure rate of the different moxidectin treatment regimens against co-infection.
 
	
	7) trial A: to determine the population PK parameters of the optimal dose of moxidectin in the treatment of S. stercoralis.	
	
 
8) trial B: to relate socioeconomic characteristics (possession of indicator assets), access to sanitation, water facilities, and hygiene and environmental reservoirs behaviour to infection intensity
 
	
Study design	Single blinded, randomized controlled trial (trial A) (participants and lab technicians are blinded); double blinded randomized controlled non-inferiority trial (trial B)	
Study product / intervention	Administration of a single oral dose of moxidectin or ivermectin	
Comparator(s)	Matching placebo (trial A, B), Ivermectin (trial B)	
Key inclusion / Exclusion criteria	Inclusion: Adults ( $\geq$ 18, <65 years) infected with S. stercoralis , absence of major systemic illnesses, written informed consent signed by individual	
	Exclusion: Any abnormal medical conditions or chronic disease, negative diagnostic result for S. stercoralis , no written informed consent by individual. Pregnant women, lactating women or women planning to become pregnant within the next six months	
Primary Endpoints	CR on S. stercoralis	
Secondary Endpoints	LRR against S. stercoralis , safety and pharmacokinetic parameters in S. stercoralis infected populations	

Exploratory Endpoints	Co-infection
Interim Analyses	None
Study Duration	8 weeks (trial A) / 8 weeks (trial B)
Schedule	08/2019 of first-participant in (planned) 08/2021 of last-participant out (planned)

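### As written, the slide quality check in 4.3.1 passes a Kato-Katz slide read as 0 by one reader and 1–10 eggs by the other, although the slide's positive/negative call is reversed

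*Combined protocol and SAP*

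**What the plan says.** Section 4.3.1 puts Baermann and Kato-Katz slides through one quality-control rule. After the technicians' reading, an "independent quality control of sample results (approximately 10%) will be conducted". A result is accepted as correct when two conditions hold:

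- Criterion (i) is "No difference in presence/absence", followed by the name *S. stercoralis* and no other species.
- Criterion (ii) is that "egg/larvae counts are +/-10 eggs/larvae for counts <100 eggs/larvae or +/-20% for counts >100 eggs/larvae", applied to each species separately.

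On failure, the rule is: "In case discrepancies above the tolerance margin are noted in one or more slides, all slides are re-read by the local technicians". Discordant results are then discussed to reach consensus. The slides "will be destroyed within one day (after passing the quality control").

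The same section says that, from two stool samples per participant, "a duplicate Kato-Katz thick smear will be prepared to detect co-infection" with *A. lumbricoides*, *T. trichiura* and hookworm. Eggs are recorded by species and "qualitatively assigned as egg positive or negative".

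The synopsis lists as secondary objective 6 "to evaluate the cure rate of the different moxidectin treatment regimens against co-infection". Section 4.1 and the endpoint rows of the synopsis class the co-infection result as exploratory, and the objectives in Section 3 do not mention it. Section 7.3 describes cure in general terms as conversion from worm-positive to worm-negative.

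**The concern.** A cure rate rests on a yes/no call, and a tolerance of ten either way does not protect that call when counts are near zero. Criterion (i) gives *S. stercoralis* the extra protection it needs. The three Kato-Katz species also have a planned cure rate, but as written they have only the count margin.

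At stake is whether quality control can detect the one kind of reading error that matters most for a positive/negative outcome. A slide that passes is discarded within a day, so a disagreement accepted under the margin cannot be resolved later. No other check covers it: the 15% data check in Section 10.1 compares entries with the hard copy and cannot detect a misread slide.

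**Working it through.** The plan gives no figure on this point to reproduce. The check applies the written rule to pairs of readings and then sizes the quality-control sample.

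**Step 1: the rule applied to a reading of 0 against a reading of n.** Both readings are below 100 for the values considered, so the margin of 10 applies whichever reader is taken as reference.

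- Kato-Katz species, criterion (ii) only: pass if |0 − n| ≤ 10. Each n from 1 to 10 passes; n = 11 is the first failure.
- *S. stercoralis*, criteria (i) and (ii): any n ≥ 1 is a presence/absence difference, so n = 1 is the first failure.

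Ten pairs (0 versus 1, up to 0 versus 10) are therefore accepted for a Kato-Katz species and rejected for *S. stercoralis*. In each of the ten, one reader calls the slide negative and the other calls it positive.

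**Step 2: from slide to participant.** Sections 4.3.1 and 4.3.4 and footnote (a) of Table 1 give 2 stool samples × 2 smears = 4 Kato-Katz slides per participant and time point. If any of the other three slides is positive for that species, the participant is positive whichever reading of the disputed slide stands. Status depends on the disputed slide only when all three others are negative.

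**Step 3: size of the checked set.** Inputs are 210 and 350 enrolled participants, 4 slides each, and about 10% checked. The calculation assumes that the 10% applies evenly to Kato-Katz slides; the sampling unit is not stated.

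- Trial A: 210 × 4 = 840 slides; 10% is 84.
- Trial B: 350 × 4 = 1,400 slides; 10% is 140.

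These are per time point and before drop-out. Slides from people screened but not enrolled are extra, and their number is not given.

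**Step 4: illustrative number of such disagreements.** The documents give no co-infection egg counts and no reader-error rates. Purely as an assumption, let 1% to 5% of checked Kato-Katz slides be discordant in this way:

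- Trial A: 84 × 0.01 = 0.8 to 84 × 0.05 = 4.2, or about 1 to 4 slides per time point.
- Trial B: 140 × 0.01 = 1.4 to 140 × 0.05 = 7.0, or about 1 to 7 slides per time point.

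This range shows the workload of a fix. It does not estimate how often the error occurs.

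**Step 5: with the change.** If criterion (i) covered every species, all ten pairs in Step 1 would fail and be re-read, as they already are for *S. stercoralis*.

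**The case against.** The strongest reply is that this is a wording slip. Criterion (i) is terse and ungrammatical, and the reference cited for the rule is, by its title, about quality control of Kato-Katz readings for *Trichuris* and *Ascaris*. The authors may have meant all species. This stands as a possibility, and the source cannot be consulted here. Technicians, however, apply the words in front of them; if all species were meant, the edit only states that intention.

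A second reply is that weighting quality control towards the primary parasite is reasonable, that co-infection cure is exploratory, and that about 90% of slides are never checked. All of this is true and limits the weight of the point. It does not explain why a slide that is checked should be accepted with opposite calls.

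Third, the link to a cure definition is partly inferred. Section 7.3 gives one generic sentence, the parallel synopsis sentence speaks of larvae, and no separate rule is given for co-infection. The quality-control rule sits in the baseline section and is not repeated in 4.3.4, so its use at follow-up is also inferred. Both limits stand.

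A reader might go further and infer that participants' co-infection status, or the reported co-infection cure rates, will be wrong. The documents do not support that: only the slide-level call is certain to reverse, and no rate can be derived. Nor can one infer any effect on the *S. stercoralis* cure rate, because criterion (i) protects it explicitly.

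**Conclusion.** The point holds as a minor gap in a stated rule. Read literally, 4.3.1 accepts any Kato-Katz disagreement from 0 versus 1 up to 0 versus 10 eggs, in either reader order, while rejecting every such disagreement for *S. stercoralis*. That result follows from the text alone.

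Its consequence for co-infection cure depends on facts the documents do not give: how common low egg counts are, how often readers disagree, and how often the participant's other three slides are negative. It also rests on two inferences, that the rule applies at follow-up and that co-infection cure is judged as positive to negative. No effect on the primary endpoint or on any trial conclusion is shown. The change is worth making because it is cheap, not because harm has been demonstrated.

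**What to change.** In 4.3.1 and the laboratory procedure, reword criterion (i) so that the two readers must agree on presence or absence of *S. stercoralis* and of each Kato-Katz species, and state that this applies at baseline and follow-up. For this added trigger, re-read at least the discordant slide and whichever of that participant's Kato-Katz slides still exist. Leave the count margins and the existing trigger for re-reading all slides as they are; restricting the added trigger avoids a full re-read for every low-count disagreement.

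The discordant slide will be available, because slides are discarded only after passing and under the new wording it has not passed. Slides from the participant's other stool sample may already be gone.

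The cost is one clause and some extra reading: on the assumed 1–5% discordance, about 1–4 discordant slides in trial A and 1–7 in trial B per time point, plus the surviving companion slides. Slides already destroyed cannot be recovered, so the change helps only slides still to be read. Protocol version 2.2 is dated July 2020, first enrolment was planned for August 2019, and the synopsis already names 8 mg as the trial A dose, so in practice this may mean trial B alone. Sample size, power and the primary analysis do not change.

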#### 4.3.2. Physical and clinical examination

At baseline, the medical history of *S. stercoralis*-infected participants in the study will be assessed with a clinical and physical examination carried out by the study clinician, who will assess weight, height, body temperature, pulse rate, blood pressure. Hemoglobin (Hb) levels will be detected using HemoCue to exclude severely anemic participants (below 80 g/l in adults according WHO) [31]. To avoid accidental treatment of pregnant women all female participants will be asked to provide a urine sample of at least 10 ml to be subjected to a pregnancy RDT. Women will be individually counselled that they should not become pregnant during the entire study period and will be interviewed if they are currently breastfeeding or planning to become pregnant. Any symptoms and abnormalities prior to treatment will be recorded on the case report form (CRF).

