Today, chemotherapy combined with health education programs, remain the core to reduce the serious health impacts. The currently advocated treatments by the World Health Organization (WHO) are a single dose of ivermectin or multiple doses of albendazole, which has a lower efficacy compared to ivermectin [9, 10]. Since drug resistance is a threat and the drug pressure is high it is of uttermost importance to develop new treatment alternatives. Among new candidates in the human anthelminthic drug development pipeline, moxidectin, a macrocyclic lactone might be an excellent alternative. Moxidectin has been approved recently by the Food and Drug Administration (FDA) for use against onchocerciasis. (http://www.who.int/tdr/news/2018/moxidectin-approved-as-treatment-for-river-blindness/en/) [11]. The drug offers some advantages over ivermectin. First of all, moxidectin is used weight independent (for onchocerciasis at an 8 mg fixed dose), which renders the administration easier to handle, especially when treating large communities. Second, moxidectin has been shown to have a lower neurotoxic potential than ivermectin [12]. Thirdly, the pharmacokinetic profile of moxidectin in healthy individuals (very long  $t_{1/2}$ , and a large Vd/F, compared to ivermectin) arises prospects for efficacy also against long-term parasitic activity – as is particularly important when treatment of *S. stercoralis* is desired [13]. Finally, most importantly moxidectin has been used successfully in veterinary medicine against ivermectin-resistant strains [14].

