The clinical significant adverse advents of moxidectin are though very similar to those of ivermectin and a consequence of excessive concentration. The drug is typically used as a single oral dose (8 mg) in patients aged 12 years and older and evaluated as an extremely safe drug. Most common side effects include hypotension, itching, headache, abdominal pain, fever, dizziness or diarrhea. Serious or even fatal encephalopathy may occur in patients coinfected with Loa Loa. Furthermore, moxidectin is known to worsen onchodermatitis in patients with hyperactive onchodermatitits. Laos and Cambodia are not endemic neither for Loa Loa nor onchodermatitits and thus these symptomatic advents shall not constitute a risk in our study. Nevertheless patients with symptoms for onchodermatitits (severe itching, bumps under the skin, blindness) will be excluded from the study. Additionally, although conclusive teratogenic data on moxidectin are missing, decreased fetal survival and increased fetal born with malfunctions is observed in some animals studies. Thus we do not see it recommended using moxidectin with pregnant female and pregnant patients will strictly be excluded. Last, owing to the lipophilic nature of moxidectin, extraction of moxidectin to the breast milk of nursing mothers is very likely and could be demonstrated in lactating cows. The risk of moxidectin in nursing infants is though unknown. Breastfeeding females will be excluded in this study.

In a small exploratory study using the veterinary formulation, a single dose of 8 mg of moxidectin, and a small sample size (127 participants) moxidectin has been found to be efficacious against *S. stercoralis* (cure rates of 93.7%) and its tolerability confirmed also in patients [15].

Yet, despite the attractive attributes of moxidectin and its promising potential in the treatment of *S. stercoralis* it remains off-label. First of all, the efficacy of the human formulation against *S. stercoralis* infections has not been assessed to date, neither has the optimal dosage been elucidated. A single dose of 36 mg moxidectin in healthy adults was the highest single dose tested to date that still represented a well-tolerated dose [13]. The 12 mg, therefore, selected as the highest dose in our study to elaborate a dose-response relationship for the use of moxidectin in *S. stercoralis* infections will not pose any health risk.

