#### 4.3.4. Assessment of efficacy after treatment

The efficacy of the treatment will be determined 28 days post-treatment by collecting another three stool samples, which will be microscopically examined for *S. stercoralis* applying each duplicate Baermann technique as well as for potential co-infection with *A. lumbricoides*, *T. trichiura* and hookworm eggs using each duplicate Kato-Katz thick smears on two stool samples.

Participants will be considered *S. stercoralis* cured if no larvae have been found in any of the stool samples. Infection was calculated as larvae per gram stool. LPG will be assessed by calculating the mean of the larvae counts from the three duplicate Baermann assays and adjusted to the previously weighted used amount of stool sample. At the end of the study (day 21) all participants remaining positive for *S. stercoralis* will be treated with ivermectin (200  $\mu$ g/kg), the current standard drug against *S. stercoralis* [9].

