## 4.5. Study duration and duration of subject participation

The trial will last a maximum of 2 months, each (trial A and B). The screening for the baseline will start four weeks prior to the treatment. Follow up screening will take place 3-4 weeks post-treatment. Schedules of visits are summarized below (Table 1).

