#### Exclusion criteria

1. Presence of acute or uncontrolled systemic illnesses (e.g. severe anemia) as assessed by a medical doctor, upon initial clinical assessment.

2. History of severe chronic disease or major systemic illnesses, e.g. severe anemia, severe chronic heart, liver or renal disease as asked by the medical doctor, upon initial clinical assessment.

- 3. Prior treatment with anthelmintics (eg, diethylcarbamazine [DEC], suramin, ivermectin, mebendazole or albendazole) within 4 weeks before planned test article administration.
- 4. Attending other clinical trials during the study.

5. Positive pregnancy test, lactating women and/or women planning to become pregnant within the next 6 months.

Participants who were diagnosed with a STH infection, but who were excluded from the study due to one or several of the above-mentioned exclusion criteria, including withdrawals will be offered standard anthelminthic treatment. Participants suffering from clinical malaria (fever plus positive diagnostic test) will be treated according to national guidelines.

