#### 7.3. Description of statistical methods

An available case analysis (full analysis set according to the intention to treat principle) will be performed, including all subjects with primary end point data. Supplementary, a per-protocol analysis will be conducted. CRs will be calculated as the percentage of worm-positive adults at baseline who become worm-negative after treatment. LPG will be assessed by calculating the mean of the larvae counts from the three duplicate Baermann assays and relate this value to the mean weighted amount of stool sample. The LRR will be calculated (LRR = (1-(mean at follow-up/mean at baseline))\*100).

AEs will be evaluated descriptively as the difference of proportion reporting adverse events before and after treatment.

Trial A:  $E_{max}$  models using the Dose Finding package of the statistical software environment R will be implemented to predict the dose-response curves in terms of CRs and LRRs. Noncompartmental and nonlinear mixed-effects (NLME) modeling will be used to determine pharmacokinetic parameters.

On the basis of the LC-MS/MS measurements, the following PK parameters for plasma, whole blood and capillary blood will be calculated:

• Cmax maximal plasma concentration

- tmax time to reach Cmax
- AUC area under the curve, from 0 to 24h and 0 to inf.
- t1/2 elimination half-life

 $C_{max}$  and  $t_{max}$  will be observed values derived from the plasma concentration time profile. AUC and  $t_{1/2}$  will calculated with the software WinNonlin (Version 5.2, Pharsight Corporation, USA) using compartmental analysis. The elimination half-life will be estimated by the equation:  $t_{1/2} = ln2/\lambda$ , where  $\lambda$  will be determined by performing a regression of the natural logarithm of the concentration values during the elimination period.

Trial B: The non-inferiority margin is set to 10%-points, i.e. if the lower bound of the 95% CI of the differences in cure rates is greater than -0.1 we conclude that moxidectin is non-inferior to ivermectin. The 95% confidence interval of the differences in CRs will be estimated using the standard formula:

 $CI = (CR_{mox} - CR_{iver}) + - Z_{a/2} * \sqrt{(SE_{mox}^2 + SE_{iver}^2)}.$ 

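### Section 4.3.2 limits pregnancy-avoidance counselling to the study period, which ends 21-28 days after dosing; it should state a post-dose period, by default six months from the dose

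*Combined protocol and SAP*

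**What the plan says.** Section 4.3.2 requires a urine pregnancy test for all female participants, an interview on breastfeeding and pregnancy plans, and individual counselling that "they should not become pregnant during the entire study period". It gives no number of days or months after dosing.

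The study period is not formally defined, but several places fix its end:
- Section 4.3 gives a follow-up of 21-28 days.
- Section 4.5 states: "Follow up screening will take place 3-4 weeks post-treatment". It caps each trial at two months, with screening starting four weeks before treatment.
- The last visit in Table 1 (Section 4.6) is day 28.
- Section 4.3.4 ties the end of the study to day 21, in the sentence on rescue treatment that begins "At the end of the study (day 21) all participants remaining positive for".

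Exclusion criterion 5 covers "women planning to become pregnant within the next 6 months", and the Synopsis has the same horizon ("women planning to become pregnant within the next six months").

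On hazard, Section 2 says that "although conclusive teratogenic data on moxidectin are missing, decreased fetal survival and increased fetal born with malfunctions is observed in some animals studies". It also lists among the drug's advantages "the pharmacokinetic profile of moxidectin in healthy individuals (very long" half-life, relative to ivermectin, without giving a figure.

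**The concern.** The protocol treats fetal exposure to moxidectin as something to prevent. It excludes pregnant women, excludes those planning pregnancy within six months, and counsels the rest. It also counts on the drug's persistence as a benefit. The counselling, however, is tied to the end of follow-up and not to the dose or to how long the drug stays in the body.

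The women left without visible advice are those who were correctly enrolled, with a negative test and no plan to conceive, and who then become pregnant unintentionally or change their plans after the last visit. At stake is participant safety and the consistency of the protocol with its own reasoning. No estimate or test is involved.

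**Working it through.** The plan states no figure that could be reproduced here, so the check is date arithmetic followed by an illustrative elimination calculation.

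**1. Calendar comparison.** Inputs: end of study at day 21 (Section 4.3.4) or day 28 (Table 1), and a six-month horizon (exclusion criterion 5).
- Six months = 6 × 365.25 / 12 = 182.6 days.
- After day 28: 182.6 − 28 = 154.6 days (5.1 months). After day 21: 182.6 − 21 = 161.6 days (5.3 months).
- Share of six months covered by counselling: 21 / 182.6 = 11% to 28 / 182.6 = 15%.

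The criterion does not say when its six months start. Counted from screening at day −28, they would end 154.6 days after dosing, leaving 154.6 − 28 = 126.6 days after day 28. New text should therefore count from the dose.

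**2. Does other text fill the interval?**
- Exclusion criterion 5 asks about intention at entry. It gives an enrolled woman no instruction.
- Section 6.1.5 lists congenital anomaly or birth defect as a serious adverse event, and requires possibly related serious events after the study period to be recorded and reported. That is reporting after the fact, not prevention, and it depends on the event reaching the study team.
- No other available protocol text sets a post-dose avoidance period or a contraception requirement.

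**3. Illustration of persistence.** Assumptions, none of them in the documents: mono-exponential decline, washout taken as five half-lives, and the half-lives tabulated. Percent remaining = 100 × 0.5^(t / half-life).

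| Assumed half-life (days) | Five half-lives (days) | Remaining at day 21 | Remaining at day 28 | Remaining at six months |
|---|---|---|---|---|
| 5 | 25 | 5.4% | 2.1% | 0.0% |
| 10 | 50 | 23.3% | 14.4% | 0.0% |
| 20 | 100 | 48.3% | 37.9% | 0.2% |
| 30 | 150 | 61.6% | 52.4% | 1.5% |
| 40 | 200 | 69.5% | 61.6% | 4.2% |

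Longest half-life for which five half-lives fit: 21 / 5 = 4.2 days for day 21; 28 / 5 = 5.6 days for day 28; 182.6 / 5 = 36.5 days for six months.

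**4. Could trial A justify a shorter period?** Section 7.3 plans to estimate the half-life ("The elimination half-life will be estimated by the equation" that follows there). Section 4.3.5 ends blood sampling at day 28. For assumed half-lives of 20 to 40 days, that spans 28 / 20 = 1.4 down to 28 / 40 = 0.7 half-lives, a poor basis for a terminal half-life.

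**The case against.** Four objections deserve weight.

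First, the consent pages were not available, and pregnancy advice for participants may well be there; Section 9.3 says that all participants are individually informed of benefits and risks. A reader might infer that women receive no advice beyond follow-up. The documents do not support that. What stands is narrower: Section 4.3.2, which directs the counselling, states only the study period.

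Second, six months is an enrolment screen and the protocol gives no reason for it. A reader might take it as the protocol's own washout or risk horizon, with five months of it left unprotected. That is not supported either. The screen and the counselling serve different purposes, so the 155-162 days measure a difference in calendar scope and nothing more.

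Third, the elimination table is built on assumptions. The documents give no half-life, no exposure threshold and no doses for the animal studies, and percent remaining is not fetal exposure or harm. This objection stands in full. The table shows only how sensitive the answer is to the half-life.

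Fourth, safeguards exist: the pregnancy test, the interview, the intention screen, and the reporting of birth defects after the study period. They narrow the group concerned, and for unintended pregnancy one more sentence of advice may change little. They still do not tell an enrolled woman how long to avoid pregnancy after the dose.

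**Conclusion.** The point holds as a matter to consider, with medium confidence. The protocol's counselling rule stops 21-28 days after dosing, while the same protocol cites adverse fetal findings in animals, a very long half-life and a six-month intention screen. Neither the intention screen nor the reporting rule closes that interval.

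The size that can be stated is 155-162 days of a six-month horizon counted from the dose. This rests on reading the study period as ending at day 21 or day 28, which the visit schedule supports. Even if the whole two-month maximum were counted after dosing (2 × 365.25 / 12 = 60.9 days), it would cover five half-lives only up to 60.9 / 5 = 12.2 days, under the same assumed rule.

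Neither the fetal risk nor the number of women affected can be stated from the documents. Anyone reading the point as evidence of demonstrated harm, or as a threat to the trial's results, would go too far: endpoint, sample size and analysis are untouched.

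**What to change.** In Section 4.3.2, advise all women not to become pregnant during the study and for six months after the dose. Six months is a default consistent with exclusion criterion 5, not a derived washout. Use the same instruction in both arms of trial B, which Section 4.2 describes as double blinded. Align the consent sheet if it does not already say this. If the sponsor prefers a shorter period, state it and justify it from established terminal half-life data, not from trial A's sampling to day 28 alone.

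The cost is one sentence, an update of the English, Lao and Khmer sheets if needed (Section 9.3), and ethics approval before use (Section 8.1) from the committees in Switzerland, Laos and Cambodia (Section 9.1). No visit or procedure is added. Section 3 already names 8 mg as the outcome of trial A, so the change may reach only trial B. There, women among the 175 ivermectin participants would receive advice aimed at moxidectin that they may not need. Some women may decline to take part; the documents allow no estimate of how many.
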